3.3.2.8 Concomitant Medications

All concomitant medications taken during the conduct of the study, including those taken for AEs or other medical events, should be recorded in the subject's source documents and captured in the eCRF as required.

3.3.2.9 Hospitalization due to Cardiopulmonary Indications

Hospitalizations due to cardiopulmonary indications must be recorded in the eCRF from the time of informed consent until study termination. Adverse events resulting in hospitalizations, regardless of cause or duration should also be recorded as SAEs per Appendix 15.2. Please note that, when possible, study medication should be continued during hospitalizations.

3.3.2.10 Exacerbations of Underlying Lung Disease

An exacerbation of underlying lung disease is defined as an acute, clinically significant, respiratory deterioration characterized by evidence of new widespread alveolar abnormality (Collard 2016). As adapted from the publication by Collard and colleagues (Collard 2016), the following diagnostic criteria may be used to help support a diagnosis of acute exacerbation:

- 1. Previous or concurrent diagnosis of ILD including CPFE
- 2. Acute worsening or development of dyspnea typically of less than 1 month duration
- 3. Computed topography (CT) with new bilateral ground-glass opacity and/or consolidation superimposed on a background pattern consistent with usual interstitial pneumonia pattern
- 4. Deterioration not fully explained by cardiac failure or fluid overload

For the purposes of this protocol, events that are clinically considered to meet the definition of acute exacerbation but fail to meet all 4 diagnostic criteria due to missing CT data should still be considered an exacerbation for reporting purposes.

Exacerbations of underlying lung disease should be recorded throughout the duration of the study from the time of informed consent until study termination. Exacerbations of underlying lung disease will also be reported as AEs or SAEs per Appendix 15.2.

3.3.2.11 Weekly Telephone/Email Contact

Weekly telephone/email contact is required throughout the 16-week study to instruct the subject to titrate their dose of study drug and to assess for AEs and concomitant medications. Weekly telephone/email contact may be replaced by a face-to-face interaction on the weeks where study visits occur and the information can be obtained during the visit). The subject may be contacted via email in lieu of a telephone call; however, email should not replace direct follow-up by telephone or in clinic for clinically significant AEs or other emergent issues. All telephone or email contacts (ie, any dosing instructions, AEs reported and/or medication changes) with the subject must be noted in the source documentation.

3.4 NUMBER OF SUBJECTS

Using an allocation ratio of 1:1 between inhaled treprostinil and placebo, a sample size of approximately 266 subjects (133 per treatment) would provide at least 90% power at a significance level of 0.05 (2-sided hypothesis) to detect a 30 meter between-treatment difference in the change from Baseline to Week 16 in 6MWD assuming a standard deviation of 75 meters. The total sample size will be approximately 314 subjects to account for a discontinuation rate of approximately 15%.

3.5 NUMBER OF CENTERS

This study is multicenter with approximately 120 participating study centers.

3.6 ESTIMATED STUDY DURATION

From Screening until study completion, expected duration of study participation is approximately 20 weeks (includes a 4-week Screening period and 16-week Treatment Phase).

4 SUBJECT ELIGIBILITY

Inclusion and exclusion criteria are to be assessed during the Screening period and reconfirmed at the Baseline Visit prior to the first dose of study drug. Study related procedures must be conducted during the Screening period after obtaining informed consent to determine subject eligibility for the study.

4.1 INCLUSION CRITERIA

- 1. Subject voluntarily gives informed consent to participate in the study.
- 2. Males and females aged 18 years or older at the time of informed consent.
 - a. Females of reproductive potential¹ must be non-pregnant (as confirmed by a urine pregnancy test at screening) and non-lactating, and will:
 - i. Either abstain from intercourse (when it is in line with their preferred and usual lifestyle), or
 - ii. Use 2 medically acceptable, highly-effective forms of contraception² for the duration of study, and at least 30 days after discontinuing study drug.
 - b. Males with a partner of childbearing potential must use a condom for the duration of treatment and for at least 48 hours after discontinuing study drug.
- 3. The subject has a confirmed diagnosis of WHO Group 3 PH based on CT imaging, which demonstrates evidence of diffuse parenchymal lung disease performed within 6 months prior to randomization. Subjects may have any form of ILD or CPFE.
- 4. Subjects are required to have a RHC within 1 year prior to randomization with the following documented parameters:
 - a. Pulmonary vascular resistance (PVR) > 3 Wood Units (WU) and
 - b. A pulmonary capillary wedge pressure (PCWP) of \leq 15 mmHg and
 - c. A mean pulmonary arterial pressure (mPAP) of \geq 25 mmHg
- 5. Baseline 6MWD \geq 100 meters.
- 6. Subjects on a chronic medication for underlying lung disease (ie, pirfenidone, nintedanib, etc) must be on a stable and optimized dose for ≥ 30 days prior to randomization.
- 7. In the opinion of the Investigator, the subject is able to communicate effectively with study personnel, and is considered reliable, willing and likely to be cooperative with protocol requirements, including attending all study visits.
- 8. Subjects with connective tissue disease (CTD) must have a Baseline FVC of < 70%.

4.2 EXCLUSION CRITERIA

- 1. The subject has a diagnosis of PAH or PH for reasons other than WHO Group 3 PH-ILD as outlined in inclusion criterion 3.
- 2. The subject has shown intolerance or significant lack of efficacy to a prostacyclin or prostacyclin analogue that resulted in discontinuation or inability to effectively titrate that therapy.

Females who are successfully sterilized (surgical sterilization methods include hysterectomy, bilateral tubal ligation, or bilateral oophorectomy) or are postmenopausal (defined as amenorrhea for at least 12 consecutive months) are not considered to be of reproductive potential.

Medically acceptable, highly-effective forms of contraception can include approved hormonal contraceptives (oral, injectable, and implantable), and barrier methods (such as a condom or diaphragm) when used with a spermicide. For women of reproductive potential, a negative pregnancy test is required at Screening and Baseline prior to initiating study drug.

- 3. The subject has received any PAH approved therapy including: prostacyclin therapy (ie, epoprostenol, treprostinil, iloprost, or beraprost; except for acute vasoreactivity testing), IP receptor agonist (selexipag), endothelin receptor antagonist (ERA), phosphodiesterase type 5 inhibitor (PDE5-I), or soluble guanylate cyclase (sGC) stimulator within 60 days of randomization.
- 4. The subject has evidence of clinically significant left-sided heart disease as defined by:
 - a. PCWP > 15 mmHg
 - b. Left ventricular ejection fraction < 40%.

Note: Subjects with abnormal left ventricular function attributable entirely to impaired left ventricular filling due to the effects of right ventricular overload (ie, right ventricular hypertrophy and/or dilatation) will not be excluded.

- 5. The subject is receiving > 10 L/min of oxygen supplementation by any mode of delivery at rest at Baseline.
- 6. Current use of any inhaled tobacco/marijuana products or significant history of drug abuse at the time of informed consent.
- 7. Exacerbation of underlying lung disease or active pulmonary or upper respiratory infection within 30 days of randomization.
- 8. Initiation of pulmonary rehabilitation within 12 weeks prior to randomization.
- 9. In the opinion of the Investigator, the subject has any condition that would interfere with the interpretation of study assessments or has any disease or condition (ie, peripheral vascular disease, musculoskeletal disorder, morbid obesity) that would likely be the primary limit to ambulation (as opposed to PH).
- 10. Use of any investigational drug/device, or participation in any investigational study with therapeutic intent within 30 days prior to randomization.
- 11. Severe concomitant illness limiting life expectancy (< 6 months).
- 12. Acute pulmonary embolism within 90 days of randomization.

4.3 PRESCRIBED THERAPY

Subjects must not be receiving any prostacyclin (ie, epoprostenol, treprostinil, iloprost, beraprost, or any other prostacyclin therapy) within 60 days prior to randomization (unless used for acute vasoreactivity testing) until study termination. Subjects must also not be receiving any other FDA approved PAH background therapies including: an IP receptor agonist, ERA, PDE5-I, and/or sGC stimulator within 60 days of randomization through the permanent discontinuation of study drug or study termination.

Subjects on a chronic medication for underlying lung disease (ie, pirfenidone, nintedanib, etc) must be on a stable and optimized dose for ≥ 30 days prior to randomization. Subjects may

not newly initiate pirfenidone or nintedanib from randomization through the permanent discontinuation of study drug or study termination.

Subjects may not initiate pulmonary rehabilitation (rehab) within 12 weeks prior to randomization until the permanent discontinuation of study drug or study termination.

All concomitant medications taken during the conduct of the study, including those taken for AEs or other medical events, should be recorded in the subject's source documents and transcribed into the eCRF as required. The flow rate of supplemental oxygen should be recorded as outlined in Section 3.3.2.6.2.

5 SUBJECT ENROLLMENT

5.1 TREATMENT ASSIGNMENT

Subjects will be randomized (1:1) to receive treatment with inhaled treprostinil (6 mcg/breath) or placebo.

5.2 RANDOMIZATION

Subjects will be randomized (1:1) to receive treatment with inhaled treprostinil (6 mcg/breath) or placebo. An IXRS will be utilized for the central randomization procedure. Sites will enter values of the qualifying 6MWT and the date the test was conducted into the IXRS and will be notified if the subject qualifies for the study.

All subjects will be randomized using a centrally administered stratified permuted block randomization, stratified by Baseline 6MWD (\leq 350 meters and > 350 meters).

Prior to randomization, site personnel should complete a Pre-Baseline Review Form for review and approval by the Medical Monitor.

5.3 BLINDING

The Investigator, study site, subject and Sponsor will not be aware of the treatment allocation. All clinical study material will be provided as blinded study drug.

6 DRUGS AND DOSING (OR TREATMENT PROCEDURES)

6.1 DRUG DOSAGE, ADMINISTRATION, AND SCHEDULE

Treprostinil for inhalation solution (0.6 mg/mL) is delivered via an ultrasonic nebulizer which emits a dose of approximately 6 mcg per breath. Placebo will be provided as an identical solution that will be inhaled using the same ultrasonic nebulizer. All subjects will receive study drug (inhaled treprostinil or placebo) using the commercially available TD-100 ultrasonic nebulizer (Tyvaso Inhalation System®). Subjects will be trained on inhalation of study drug using the nebulizer device. Detailed instructions for the use of these devices will be provided to all study subjects. In addition, all subjects will receive a copy of the commercially available Tyvaso Inhalation System Instructions for Use (IFU) for the TD-100 ultrasonic nebulizer.

Once informed consent has been signed, all entry criteria have been met, and the randomized treatment assignment confirmed, the first dose of study drug (3 breaths; 18 mcg) will be inhaled in the clinic, followed by at least a 1 hour observation period (defined as Day 1). Study drug doses should be maximized throughout the study, dose escalations (additional 1 breath 4 times daily) can occur up to every 3 days with a target dosing regimen of 9 breaths (54 mcg) 4 times daily and a maximum dose of 12 breaths (72 mcg) 4 times daily within 4 weeks of beginning the treatment, as clinically tolerated. Table 6-1 provides a guideline for the recommended dose escalations.

Table 6-1 Recommended Inhaled Treprostinil Dose Escalation Table

Study Day ^a	Single Dose	Total Daily Dose					
	Titrating to maximum dose of 12 breaths						
1-3	3 breaths QID (18 mcg)	72 mcg					
4-6	4 breaths QID (24 mcg)	96 mcg					
7-9	5 breaths QID (30 mcg)	120 mcg					
10-12	6 breaths QID (36 mcg)	144 mcg					
13-15	7 breaths QID (42 mcg)	168 mcg					
16-18	8 breaths QID (48 mcg)	192 mcg					
19-21	9 breaths QID (54 mcg)	216 mcg					
22-24	10 breaths QID (60 mcg)	240 mcg					
25-27	11 breaths QID (66 mcg)	264 mcg					
28 (and beyond)	12 breaths QID (72 mcg)	288 mcg					

Abbreviations: QID, 4 times daily; mcg,: micrograms

a Study day refers to the days on study drug with Day 1 referring to the first dose of study drug.

The dosing schedule is recommended as a guide only. The Investigator may determine the appropriate dosing schedule on an individual subject basis, considering tolerability and functional improvement.

If subjects are unable to tolerate the initial 3 breaths, they may decrease their next dose to 1 or 2 breaths of study drug (as determined by the Investigator) 4 times a day during waking hours. The subject will then gradually increase their dose to reach a minimum of 3 breaths, and titrate to a target dose of 9 breaths and a maximum dose of 12 breaths 4 times a day during waking hours, as clinically tolerated.

Dose changes should be conducted under appropriate medical supervision in consultation with the study site. Telephone calls/emails between the site and subject should occur prior to each dose adjustment or at least weekly to monitor for AEs, clinical worsening events, and make decisions about dose titration.

6.2 ACCESS TO BLINDED TREATMENT ASSIGNMENT

During the study, the site personnel, subject, and Sponsor will remain blinded to the treatment assignment of all subjects. A medical emergency (eg, a life threatening event) constitutes the only reason for unblinding during the Treatment Phase. Appropriate communications must take place between the site and the Sponsor before accessing the IXRS to allow unblinding of a subject's treatment assignment.

6.3 COMPLIANCE

Each subject will be provided with a dosing diary in order to record dosing information from randomization until Week 16. Subjects will be required to bring the completed dosing diary and all empty and unused study drug ampoules to each scheduled study visit. At each visit, all study drug returned by the subject (used and unused) will be collected and new study drug will be dispensed. The appropriate study personnel must document the number of used and unused ampoules and determine if the appropriate amount of study drug remains based on the dose of study drug prescribed.

Subject compliance with the prescribed dosage regimen will be monitored throughout the study. At each study visit, the subject will be asked whether he or she has been compliant

with dosing instructions. If it is determined that a subject is not compliant with study drug then site personnel must re-educate the subject on proper dosing compliance and its importance. Continued non-compliance may lead to withdrawal of the subject from the study, after consultation between the Investigator and the Sponsor.

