8 STUDY TERMINATION

8.1 CRITERIA FOR SUBJECT WITHDRAWAL

A subject may voluntarily withdraw or be withdrawn from the study and/or study drug by the Investigator at any time for reasons including, but not limited to, the following:

- The subject wishes to withdraw from further participation.
- A serious or life-threatening AE occurs or the Investigator considers that it is necessary to discontinue study drug to protect the safety of the subject.
- The subject consistently deviated from the protocol.
- Lung transplantation.
- The subject becomes pregnant.
- The subject's behavior is likely to undermine the validity of his/her results.

If a subject is discontinued from the study prematurely, the Investigator must provide an explanation in the eCRF and complete the End of Study Record for that subject. If study drug has been administered, the Investigator should make every effort to perform all scheduled evaluations prior to discharge. In the event that a subject discontinues study drug prematurely due to an AE, the subject will be followed until either the Investigator determines that the AE has resolved, it is no longer considered clinically significant, the subject is lost to further follow-up, or for 30 days if the AE extends beyond the final visit.

If a subject discontinues study drug prematurely for any reason, the subject should be encouraged to remain in the study and attend the remaining scheduled study visits (excluding the Week 15 Visit) up to and including Week 16.

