### 8.3 PREMATURE DISCONTINUATION AND MISSING DATA

#### 8.3.1 Missing Data Handling for 6MWD

For the analysis of 6MWD, subjects may not have completed the treatment with study drug prior to the Week 16 visit for the following reasons: death, progressive disease, AE, withdrawal of consent by the subject, protocol violation, loss to follow-up, termination of study by the sponsor, or withdrawal for other reasons. Every attempt must be made to perform all efficacy assessments immediately prior to premature termination of study drug or withdrawal from the study. In addition, subjects still receiving study drug may be too critically ill to perform the 6MWT, resulting in missing data for that assessment.

Every effort should be made to complete all scheduled study assessments for all randomized subjects. Although attempts will be made to continue to collect data after termination of study drug, these data are being collected for sensitivity analyses and descriptive purposes only. Assessments performed after treatment unblinding or more than 24 hours after the last dose of study drug will not be included in the main analyses of peak 6MWD.

For subjects whose peak 6MWD measures at Week 4, Week 8, Week 12, or Week 16 are missing, the missing value will be imputed as described in Table 8-1.

Reason for missing 6MWD measure	Imputation
Death (all causes)	Worst score (0 meters)
Clinical worsening event	Worst score (0 meters)
Too ill to perform 6MWT	Worst score (0 meters)
All other reasons	Last (peak) Observation Carried Forward (LOCF)

Table 8-1Imputation Rules for Peak 6MWD

Abbreviations: 6MWD, 6-Minute Walk Distance; 6MWT, 6-Minute Walk Test.

For subjects whose trough 6MWD measures at Week 15 are missing, the missing values will be imputed as described in Table 8-2.

Reason for missing 6MWD measure	Imputation
Death (all causes)	Worst score (0 meters)
Clinical worsening	Worst score (0 meters)
Too ill to perform 6MWT	Worst score (0 meters)
All other reasons	Baseline Observation Carried Forward (BOCF)

Table 8-2Imputation Rules for Trough 6MWD

Abbreviations: 6MWD, 6-Minute Walk Distance; 6MWT, 6-Minute Walk Test, BOCF, Baseline observation carried forward.

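### Protocol 6.3 and 8.1 let non-compliance or deviation end a willing subject's follow-up, in tension with the plan's aim of keeping subjects to Week 16

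*Protocol*

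**What the plan says.** **Removal.** Protocol 6.3 asks sites to re-educate a non-compliant subject and then adds: "Continued non-compliance may lead to withdrawal of the subject from the study, after consultation between the Investigator and the Sponsor". It sets no threshold. Protocol 8.1 opens with "A subject may voluntarily withdraw or be withdrawn from the study and/or study drug by the Investigator at any time". Its list of reasons includes "The subject consistently deviated from the protocol" and behaviour likely to undermine the validity of the results. For subjects discontinued after dosing, 8.1 also says "the Investigator should make every effort to perform all scheduled evaluations prior to discharge".

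**Retention.** The last paragraph of 8.1 reads: "If a subject discontinues study drug prematurely for any reason, the subject should be encouraged to remain in the study", through Week 16 and leaving out Week 15. Protocol 7.6 says the same. SAP 8.3.1 goes further: "Every effort should be made to complete all scheduled study assessments for all randomized subjects".

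**Consequences for the data.**
- SAP 8.3.1 on the main peak 6MWD analyses: "Assessments performed after treatment unblinding or more than 24 hours after the last dose of study drug will not be included". Step 1 of SAP 10.1.1.2 repeats the exclusion.
- SAP Table 8-1 gives 0 m when the walk is missing because of death, clinical worsening or being too ill to walk. Every other reason takes the last peak observation carried forward (LOCF).
- SAP 10.1.1.3 plans a sensitivity analysis that includes data collected after study drug ended.
- SAP Table 8-3 censors premature study exits at the last assessment date.
- Protocol 3.3.2.7 records adverse events until the subject is discontinued from the study. Protocol 3.3.2.9 records cardiopulmonary hospitalisations until study termination.

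**The concern.** Stopping study drug and leaving the study are different events, and only the second ends data collection. Protocol 6.3 names only the second. Protocol 8.1 leaves the choice open. A subject who misses doses but attends every visit can thus be lost to follow-up by decision of the investigator and sponsor, not by his own.

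Such missing data are avoidable, and they depend on behaviour after randomisation, which may be related to outcome. At stake are safety capture, the exploratory clinical-worsening endpoint, one planned sensitivity analysis and, for a limited set of subjects, the primary value itself.

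**Working it through.** **The plan's own figure.** The sample size reproduces and is not in question. Inputs (SAP 5): difference 30 m, SD 75 m, two-sided 0.05, 90% power.
- n per arm = 2 × (1.960 + 1.282)² × 75²/30² = 131.4, so 132. The t-based version gives 132.3, so 133, as stated.
- Power at 133 per arm is 90.4% (normal) or 90.1% (t).
- For 15% discontinuation: 133/0.85 = 156.5, so 157 per arm and 314 in total.

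**What removal changes.** Take a subject judged non-compliant around Week 8 (an example; the documents give no timing), on each of three courses:

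| Data item | Off drug, kept in study | Partly adherent, kept on drug | Removed from study |
|---|---|---|---|
| Primary Week 16 value | LOCF; 0 m if Week 16 is missing through death, worsening or being too ill | Observed walk, if within 24 hours of a dose | LOCF; 0 m only if such an event becomes known |
| Sensitivity analysis with post-drug data | Week 16 walk available | Week 16 walk available | No Week 16 walk |
| Clinical worsening | Followed to Week 16 | Followed to Week 16 | Censored at last assessment |
| New adverse events and hospitalisations | Recorded to Week 16 | Recorded to Week 16 | Not recorded after exit |

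Comparing the first and last columns, removal does not create the LOCF in the primary analysis. It loses the sensitivity-analysis walk, the later events and the chance of a correct 0 m score. Comparing the second and last, removal does replace a valid primary value. Protocol 3.3.1.1.3.1 places the peak walk 10 to 60 minutes after a dose, so a partly adherent subject still on drug would satisfy the 24-hour rule.

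Removal at Week 8 forgoes 16 − 8 = 8 of the 16 weeks of event follow-up.

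**Size of an unseen event.** If a death or worsening after exit is not known, the score is the carried walk L instead of 0 m. The shift in that arm's mean is L/157 per subject. The documents give no value for L. The assumed range is 100 m (the entry minimum) to 350 m (the stratification cut):
- 100/157 = 0.64 m
- 250/157 = 1.59 m
- 350/157 = 2.23 m

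For comparison, the standard error of the difference under the plan's assumptions is 75 × √(2/157) = 8.5 m. The shift favours whichever arm the subject is in.

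**Partly adherent subjects who would have stayed on drug.** Neither the sign nor the size of the change in the primary value is fixed. As one illustration, assume a share x of each arm is removed, the carried walk holds none of the treatment effect, and these subjects would otherwise have shown the full 30 m. The average effect is then 30 × (1 − x): 29.4 m at 2% and 28.5 m at 5%. Power with 157 per arm is 93.5% and 92.0%, against 94.3% with no removal. If the carried walk exceeds the true Week 16 value, the shift goes the other way.

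**The case against.** The strongest reply is that nothing here is mandatory. Protocol 6.3 says only that withdrawal may follow, after re-education and consultation. The retention text in 7.6 and 8.1 concerns subjects who stop drug, and it only encourages them to stay. That stands: this is a tension between discretionary clauses and not a contradiction.

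It also stands that losses are limited in several ways. Evaluations are to be attempted before exit. An exit walk after Day 99 falls in the Week 16 window of SAP Table 8-4. Adverse events already open are followed for at least 30 days and serious ones to resolution. SAP 12.2 lists deaths to 30 days after the last dose. Treatment allocation is blinded. Protocol 6.1 lets the investigator adapt the dosing schedule to tolerability, so poor tolerability need not appear as non-compliance. SAP 10.1.1.3 plans per-protocol, observed-case, MMRM and post-drug analyses. None of these recovers a visit or new event that was never recorded after exit.

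Two stronger readings are tempting, and the documents support neither.
- A reader might infer that every removal turns an obtainable Week 16 walk into LOCF in the primary analysis. One might then assume 3 to 8 of 157 active subjects removed, with carried values 30 m too high, and report a bias of 0.6 to 1.5 m (3 × 30/157 and 8 × 30/157). For a subject taken off drug, the 24-hour rule leads to LOCF whether he stays in the study or not. The rate and the 30 m excess have no source in the documents, and placebo removals are set to zero.
- A reader might infer that removal would be selective by arm, from the TRIUMPH-I rates of cough (54%) and headache (41%) in Protocol 1.2.3. Those are active-arm rates only, with no placebo rates and no adherence data. An imbalance is plausible but not shown.

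**Conclusion.** The point holds as a modest, avoidable weakness. Protocol 6.3 and 8.1 permit follow-up to end for reasons that need affect study drug at most, while 7.6, 8.1 and SAP 8.3.1 aim to keep subjects to Week 16. The main loss is new adverse-event and hospitalisation capture, clinical-worsening follow-up and the Week 16 walk for the post-drug sensitivity analysis.

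The primary analysis is affected by two routes only:
- an unseen death or worsening after exit, worth about 0.6 to 2.2 m on that arm's mean per subject under the assumed carried walk of 100 to 350 m;
- a partly adherent subject who would otherwise have stayed on drug and walked at Week 16, where direction and size are unknown.

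The documents give no removal rate, so no total effect can be stated.

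**What to change.** Reconcile Protocol 6.3 and 8.1 with the retention text.
- In 6.3, delete the words that direct the withdrawal at the study.
- In both sections, state that non-compliance, deviation or behaviour alone does not end follow-up.
- State that scheduled visits (excluding Week 15 for those off drug) and the collection of adverse events, hospitalisations, vital status and clinical worsening continue to Week 16 unless the subject withdraws consent.
- Leave decisions on study drug as they stand.
- Handle major deviators through the Per-protocol population in SAP 6, which excludes them after blinded review without ending data collection.

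This would not bring off-drug walks into the primary analysis, because SAP 8.3.1 would still exclude them. It would keep the sensitivity analysis, event capture and 0 m scoring intact.

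The cost is protocol wording, since the visits are already scheduled. The downsides are some effort to follow poorly compliant subjects, and slight dilution of the ITT estimate from partly adherent subjects who stay in.
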